Response to Diaphragmatic Pacing in Subjects with Pompe Disease

NCT02354651

Document Date: 12/05/2016

Protocol

1. Project Title

Response to Diaphragmatic Pacing in Subjects with Pompe Disease

2. Investigators:

[name], PT, PhD

Sub-Investigators:

[name], PhD

[name], PT, PhD

[name]

[name], MSN, ARNP

[name]

[name], MSN, ARNP, CPNP-PC

[name], MSN, ARNP, CPNP-PC

3. Abstract:

Diaphragm pacing is approved for replacing positive-pressure ventilators in neurodegenerative conditions including spinal cord injury and amyotrophic lateral sclerosis. Evidence shows that neurodegeneration plays a vital role to chronic ventilatory insufficiency in Pompe disease, which suggests that pacing may also benefit Pompe patients. This strategy has been shown to replace the role of mechanical ventilation during waking hours in patients with Pompe disease. The proposed study will evaluate the duration and pattern of spontaneous, versus paced ventilation in patients with Pompe disease and respiratory insufficiency. Medical records will be reviewed to document chemistry and hematology labs, chest x-ray, and review of symptoms for comorbidity. Functional outcomes include tolerance to breathing without positive pressure ventilators, and clinical and electrophysiological tests of respiratory muscle function.

4. Background:

The NeuRx DPS (Diaphragm Pacer) is a medical device approved for use in ventilator-dependent patients with spinal cord injury and patients with moderate ventilatory insufficiency due to amyotrophic lateral sclerosis. Pacing acts by bypassing the descending corticobulbar drive through the phrenic motor system to directly depolarize the diaphragm [1]. Diaphragm electrodes are implanted laparoscopically near the motor point of each hemi-diaphragm [2,3]. An external generator is connected to the externalized wire electrodes and emits an electrical impulse that directly stimulates the diaphragm muscle. In patients with phrenic neural insufficiency and yet residual contractility of the diaphragm, pacing can serve as an electrical ventilatory prosthesis, reducing or replacing positive pressure ventilation [4]. In occasional patients, spontaneous recovery of motor function has been reported after pacing, which has enabled removal of the pacing wires to restore fully independent breathing [5].

The study group will consist of twelve male or female subjects 2-65 years of age with a diagnosis of Pompe disease as defined by mutational analysis, GAA enzyme activity assay in blood spot and/or fibroblast culture less than 40% of control values, as well as clinical symptoms. In addition, subjects will be eligible if they have met the clinical eligibility for NeuRx DPS implantation. All subjects will have a history of mechanical ventilation (MV) dependence, defined as a requirement of six or more hours invasive or non-invasive MV support daily for at least 21 days in duration [10]. Subjects currently on GAA replacement therapy will continue protein replacement during the study.

Subjects will be recruited either via self-referral to the research team (e.g. after discovering the study on ClinicalTrials.gov), or referral from the surgeon who conducts the implantation surgery. The surgeon will provide subjects with the contact information of the study team, so that they may inquire to us about the study.

Exclusionary Criteria:

The subject must not:

- Be participating in another treatment study using a device for diaphragm pacing
- Be unable to complete pulmonary function testing
- Be pregnant, or become pregnant throughout participation in the study. If a subject may be pregnant, a pregnancy test will be performed, or results of a recent test will be used to confirm.

Study design:

Subjects with Pompe disease who are having NeuRx DPS implantation will be invited to participate in this study. This procedure is part of the subject's clinical care, and is not done for this or any other research project. Baseline data will be entered into the study record from clinical testing completed within 12 months of NeuRx DPS implant. After placement of DPS, study assessments will be completed at Days 3, 14, 90 and 180 per table of events on page 8.

Testing:

Pulmonary function testing equipment and test administration protocols will be standardized in accordance with ATS/ERS guidelines [12]. Pulmonary function testing will be conducted according to the schedule of assessments (page 8). During pulmonary function testing, baseline and exertional vital signs will be monitored (heart rate, respiratory rate, pulse oximetry). In addition, diaphragm EMG will be recorded, either with surface electrodes (global inspiratory muscle EMG) or by using an adaptor that enables direct EMG recording from the intramuscular pacing wires. These tests will be completed with support from any mechanical ventilation the subject may use. If the subject "sprints" routinely with reduced or no breathing support, we will also test breathing under these conditions. The following pulmonary function tests will be completed on all subjects:

Forced expiratory tests: Forced expiratory tests measure the maximal airflow and volume of gas that can be exhaled with the subject breathing or coughing forcefully. A nose clip, or cuffed tracheostomy with cuff inflated is used to prevent leakage. The subject deeply inhales and then exhales as forcefully and deeply as possible. Measurements will be obtained with the subject sitting upright and then repeated with the subject in the supine position, if tolerated. A minimum of three trials will be obtained in each position with <5% variability [13]. The highest value obtained in each position will be reported. Forced expiratory tests will be completed at Screening, Baseline, Day 14, Day 90, and Day 180.

Maximal Inspiratory Pressure (MIP): MIP will be measured with a manometer connected to the airway opening of the subject, which occludes the airway and prevents airflow. A nose clip will be used to prevent leakage and the subject is instructed to suck air from the tube with as much force as possible. Measurements will be obtained with the subject sitting upright. Transdiaphragmatic pressure (Pdi) may be calculated with esophageal and gastric manometry during MIP. The measurement will be taken three times and the best value will be reported. MIP will be completed at Screening, Baseline, Day 14, Day 90, and Day 180.

Resting Breathing Pattern: Resting ventilatory flow and timing will be recorded with a pneumotachograph and pressure transducer connected to the airway opening. If a patient

Protocol

IRB version 03.09.04

PI version V-5 Dec 5 2016

Page 3 of 11

routinely uses MV throughout the day, the sensing equipment can be placed in series to the breathing tubes. Resting breathing will be recorded under the following conditions: (1) using the subject's routine daytime ventilatory support (ventilator, BiPAP, ETC); (2) using the subject's routine daytime ventilatory support plus the diaphragm pacer; (3) using no support or the lowest support needed to maintain baseline minute ventilation (if the subject uses reduced or no settings routinely); (4) using no support or the lowest support needed to maintain baseline minute ventilation plus the diaphragm pacer (if the subject uses reduced or no settings routinely). Subjects will rest for a minimum of 30 minutes between each condition, and tests may be scheduled over two consecutive days as needed. Resting Breathing Pattern will be completed at Screening, Baseline, Day 5, Day 14, Day 30, Day 90, and Day 180. During this testing, subjects will not be taken below their lowest tolerated ventilator settings.

Respiratory Muscle Endurance Test: This test will begin after subjects rest for a minimum of one hour. Subjects will be tested in the seated position while breathing through a mouthpiece with nose clip. When a steady state breathing pattern has been reached (noted by stable tidal volumes for at least 30 seconds), subjects will be instructed how to maintain the breathing rate and volume, with the use of visual feedback on a computer. A threshold inspiratory load equivalent to 35% of the maximal inspiratory pressure will be placed on the inspiratory port of the mouthpiece. Subjects will be instructed to maintain the established breathing pattern during loaded breathing. The test will end when the subject cannot open the threshold valve for 3 consecutive breaths, or when the subject can no longer subjectively tolerate the test and must remove the mouthpiece. Loaded breathing typically lasts between 2-10 minutes. Respiratory Muscle Endurance Testing will be completed at Screening, Baseline, Day 90, and Day 180.

Magnetic stimulation: Supramaximal, cervical magnetic stimulation of the phrenic nerves will be conducted with the subjects in upright with the head and trunk supported. Stimulations will be applied from end-expiratory lung volume. At least five stimulations will be delivered at the maximum stimulator output. The resulting twitch transdiaphragmatic pressure (Pdi) will be calculated from gastric and esophageal pressures obtained by catheter-mounted transducers, and compared to reference values [14]. Magnetic stimulation will be tested at screening.

Sleep dysfunction: Breathing during sleep will be assessed using the BioRadio, which has the ability to monitor oxygen saturation, electrocardiogram, and EMG while the subject is asleep. This will occur at Baseline and Day 90. Subjects will be given a monitor, sensors, and instructions for how to set up and record during one night's sleep, which will be returned at the end of their participation.

Post-operative diaphragm conditioning:

Typically diaphragm conditioning commences after a 5-day post-operative recovery period, when post-operative pain and inflammation have been controlled for >24 hours. Diaphragm conditioning will be progressed using an ordered protocol, which consists of gradual increases in:

- (1) *The external stimulator settings.* The initial external stimulator settings will be set by the manufacturer's representative in the surgical suite, and any upper limits or restrictions in

parameters (e.g. threshold for PVC's) will be established. The stimulator settings will be increased as needed.

- (2) *The duration of diaphragm stimulation.* Starting POD#5, the pacing system will be activated for one, or more 30-minute trials, per day (maximum 5, 30 minute trials). The duration of diaphragm stimulation will be systematically increased as tolerated to accomplish three goals, including pain- and dyspnea-free pacing, overnight pacing, and continuous 24-hour pacing.
- (3) *Off-ventilator spontaneous breathing (SB).* On POD#5, the patient will undergo an initial trial of unassisted breathing with the diaphragm pacer turned on. The duration of SB with pacing will be increased to tolerance, using a protocol. If the patient cannot complete at least 30-minute bouts of paced SB, then the focus of breathing trials will be reduced pressure support mechanical ventilation.

The subject will be instructed how to operate the pacemaker equipment and be provided with a diaphragm conditioning home exercise program. This is part of the patient's routine clinical care. Diaphragm conditioning will be completed five to seven days per week by the subject, based upon the subject's daily baseline level of fatigue.

Diaphragm conditioning will routinely occur at home, yet an investigator will continue to monitor progress with the home program every 7 to 21 days by telephone. We will have experience in remote monitoring of RMST in ventilator-dependent children and adults, and remotely-supervised sessions enable investigators to monitor compliance, progress the diaphragm conditioning, and provide feedback.

SCHEDULE OF ASSESSMENTS

	SCREENING	BASELINE	D5	D14	D30	D90	D180	As Needed	Extension
Consent	X								
Resting Breathing Pattern	X	X	X	X	X	X	X	X	X
Respiratory Muscle Endurance Test	X	X				X	X	X	X
Phrenic Nerve-Magnetic Stimulation		X						X	
Maximal Inspiratory Pressure	X	X		X		X	X	X	X
Forced Expiratory Tests	X	X		X		X	X	X	X

EMG			X	X	X	X	X	X	X
Medical History/Record and Medications review, AE and Prescription Compliance assessment	ONGOING								
Questionnaires	X	X				X	X	X	
Physical exam			X	X		X	X	X	X
Sleep dysfunction measure		X				X			

Subjects will be asked to complete a daily pacemaker/ventilator diary documenting ventilator assistance use and pacemaker use. The Investigator or designee will contact the subject a minimum of two times per month to document adverse events, changes to medications, update the medical history, and assess compliance with diaphragm conditioning exercise prescription. This communication may be accomplished by email, telephone, or video conference calling.

Extension phase:

Subjects who complete this study will have the opportunity to continue in an optional extension phase, wherein they would be evaluated annually, or at the request of their physician. These evaluations can include a physical exam, EMG recording, and pulmonary function testing. This extension phase will last six years, and will allow evaluation of long-term changes in ventilator dependence.

Data analysis:

We will evaluate changes in average respiratory rate and volume, integrated EMG, and daily independent breathing time, between 0 and 6 months. Since this is an observational pilot study, data will be largely descriptive. However, the data are largely quantitative and continuous. Sample distributions and summary statistics will be calculated for each of these outcomes. Data transformations will be done if non-linear distributions exist, and repeated measures ANOVA (or non-parametric) will quantify recovery at 6 months.

7. Possible Discomforts and Risks:

Pulmonary Function Testing

Pulmonary function testing is used routinely in clinical medicine and has no inherent complications. Pulmonary function testing will be completed by the study team on Day 5, 14 and 180 after NeuRx DPS implantation. If possible, the study team will complete pulmonary function testing the day prior to NeuRx DPS implantation.

Although sustained (several minutes to several hours), intensive inspiratory loading can produce elevations in oxygen consumption, mean arterial pressure and diminish cardiac output, brief

periods of loading (<30 seconds) have not been shown to cause significant changes in cardiac parameters (Coast et al., 1988). Nevertheless, we have designed the protocol to include strict limits on baseline and exertional vital signs, in order to minimize the imposed cardiorespiratory work. Due to the brief duration of testing and training procedures, the incidence of blood gas dysfunction is extremely low. Nevertheless, end-tidal CO₂ and oxygen saturation will be monitored continually.

Respiratory testing may elicit transient fatigue or shortness of breath that resolves within several seconds of completion. Frequent rests are included to prevent or minimize these systems.

Phrenic Nerve Function Evaluation with EMG

Anterior magnetic stimulation of the phrenic nerves is a recommended technique for subjects, because it is painless and reproducible, yields supra-maximal stimulation, and does not require uncomfortable positioning [12]. Phrenic latency and compound muscle action potential (CMAP) will be determined individually for the right and left phrenic nerves [19]. The phrenic latency is the time between the stimulus and the responding diaphragm CMAP. A normal phrenic latency is between 6-8 msec in adults [20] and 4.8-8.63 msec in children [21]. The diaphragm CMAP will be recorded using surface or esophageal electrodes. Alternatively, the CMAP may be captured by recording from the implanted pacer wires. In addition to measuring CMAP, the transdiaphragmatic pressure (Pdi) may be calculated with esophageal and gastric manometry during bilateral, supra-maximal magnetic stimulation and compared to reference values obtained in healthy adults [14]. Phrenic stimulation testing will be conducted at baseline and at Day 180, unless clinical care dictates more frequent assessments are needed.

EMG recording will be completed with the implanted wires on Day 0, 5, 14, 180 and PRN.

Questionnaires

Subjects will be asked to complete the Severe Respiratory Insufficiency Questionnaire at Screening, baseline, day 90 and day 180. This questionnaire was developed for use in subjects with respiratory failure from various etiologies who utilize mechanical ventilation. It is a self-administered test that will require approximately 20 minutes to complete.

8. Possible Benefits:

There are some potential benefits to the individual subject expected in this clinical research study. The anticipated benefit to subjects and the Pompe community is to determine the mechanism of action for respiratory insufficiency and ultimately respiratory failure in Pompe disease. Subjects who participate in this clinical research study will have personalized respiratory muscle strengthening routine prescribed with regular contact with the study team.

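### Between-session change in breath volume and ventilation is not scaled to body size although subjects may be as young as 2, so growth in a child could be read as recovery

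*Protocol*

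**What the plan says.** The protocol's study-group description sets the sample at "twelve male or female subjects 2-65 years of age", with no age strata.

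Under Data analysis the protocol states: "We will evaluate changes in average respiratory rate and volume, integrated EMG, and daily independent breathing time, between 0 and 6 months". The method is that "repeated measures ANOVA (or non-parametric) will quantify recovery at 6 months". The only rescaling named there concerns distribution shape: "Data transformations will be done if non-linear distributions exist".

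The SAP (Data Interpretation) lists two kinds of between-session outcome, both analysed by repeated measures ANOVA: off-ventilator function, which it marks as primary, and breathing pattern/ventilation. It also plans within-session comparisons of volume, rate and ventilation.

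On the starting point, the protocol's Study design section says: "Baseline data will be entered into the study record from clinical testing completed within 12 months of NeuRx DPS implant".

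The available text of both documents names no percent-predicted value, z-score, per-kg scaling, height, weight or age covariate, age stratum or concurrent control. The SAP's Expected Outcomes section speaks of adults with Pompe disease, which does not match the protocol's age range.

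**The concern.** This is an uncontrolled before-after comparison. Whatever rises with time for reasons other than pacing is included in the estimated change, and the plan calls that change recovery. In adults, growth is not one of those reasons. In a child it is: breath volume and ventilation rise with body size even if respiratory muscle function stays the same.

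The SAP expects its between-session data to speak to the efficacy of pacing. If several of the twelve subjects are growing children, an increase in volume at 6 months cannot be attributed to pacing until growth is taken out. The wide baseline window adds to this, because growth accrues from the date of the baseline test and not from the date of implant.

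**Working it through.** The plan gives no power, effect size, SD, expected number of children or growth rate, so there is no figure of its own to reproduce. What follows is an illustration on stated assumptions.

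**Inputs from the documents.** Twelve subjects; ages 2 to 65; change from 0 to 6 months (Day 180); baseline test up to 12 months before implant. The longest interval is therefore 12 + 6 = 18 months. It is shorter when testing is done near implant; the protocol's risk section says the study team will test the day before if possible.

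**Assumed inputs.** Starting height h0 (cm), constant growth velocity v (cm per year), and volume proportional to height^b with b = 2.5 to 3.0.

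**Step 1: growth alone in one child.** Change in volume = [(h0 + v × T) / h0]^b − 1, with T in years.

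| h0, v | T = 0.5 | T = 1.5 |
|---|---|---|
| 87 cm, 9 cm/yr | 13% to 16% | not computed |
| 90 cm, 8 cm/yr | 11.5% to 13.9% | 36.7% to 45.6% |
| 110 cm, 6 cm/yr | 7.0% to 8.4% | 21.7% to 26.6% |
| 130 cm, 5.5 cm/yr | 5.4% to 6.5% | 16.6% to 20.3% |
| 150 cm, 5 cm/yr | 4.2% to 5.1% | 13.0% to 15.8% |
| 165 cm, 1 cm/yr | 0.8% to 0.9% | 2.3% to 2.8% |

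Example: at 90 cm over 6 months, (94/90)^2.5 = 1.115 and (94/90)^3 = 1.139. Over 18 months, (102/90)^2.5 = 1.367 and (102/90)^3 = 1.456.

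As a cross-check, take tidal volume as proportional to weight, with assumed six-month weight gains: 13.4/12.3 = 1.09 for a small child and 27/25.5 = 1.06 for an older one. That is 6% to 9% over six months, within the same range.

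**Step 2: dilution in the group.** If k of 12 subjects grow by a fraction g and pacing does nothing, the mean log change is (k/12) × ln(1 + g). For g = 8% this is a group change of 1.9% (k = 3), 3.9% (k = 6) or 8.0% (k = 12). For g = 25% it is 5.7%, 11.8% or 25.0%.

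**Step 3: chance of a nominally significant change with no pacing effect.** This was simulated with 40,000 runs per case: a two-sided 5% paired t-test on log volume (the two-time-point case of repeated measures ANOVA), n = 12. The SD of log change was assumed to be 0.20 (lower figure) or 0.10 (upper figure).

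| Growing children | g = 8% | g = 25% |
|---|---|---|
| 0 | 5% | 5% |
| 3 | 6% to 8% | 10% to 16% |
| 6 | 9% to 19% | 31% to 68% |
| 12 | 23% to 68% | 94% to 100% |

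The row with no growing children also shows the result once growth is removed by scaling.

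**Limit of steps 2 and 3.** The log scale gives every subject equal weight. On an unscaled pooled mean, with three children and nine adults whose baseline volume is m times a child's, growth of 8% in the children moves the group mean by 3 × 8% / (3 + 9m). That is 2% at m = 1 and less as m rises. Growth then biases the pooled figure less, but the pooled figure also says less about the children.

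**The case against.** The strongest reply has five parts.

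- **Few children may enrol.** Subjects unable to complete pulmonary function testing are excluded, which makes the youngest ages unlikely, and the SAP speaks of adults. With no growing children the bias is nil; with three growing 8%, the simulated error rate is 6% to 8%. This stands as a limit on size. It does not remove the point, because age 2 remains eligible.
- **The main outcome is untouched.** Off-ventilator function and daily independent breathing time are durations, not volumes that scale with size. Within-session contrasts compare conditions in the same body on the same occasion. This stands.
- **Resting volume is partly set by support.** It is recorded on the subject's usual support, or on the least support that keeps up a baseline minute ventilation. Growth need not carry through in full, so the height-based figures are illustrations. This also stands.
- **The study is a largely descriptive pilot.** True, but a descriptive change reported as recovery is open to the same misreading.
- **The plan allows transformation or a non-parametric test.** Neither removes growth. A log or rank analysis of unscaled change still contains it.

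Some stronger readings are tempting, but the documents do not support them:

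- A reader might infer that the plan commits to raw units. It does not say so; it is silent on scale.
- A reader might take "The highest value obtained in each position will be reported" as a plan to analyse unscaled spirometry over time. It only says which trial's value is kept, and forced expiratory values appear in neither named change analysis.
- A reader might set growth against the protocol's 5% variability limit. That limit governs agreement among forced expiratory trials at one test, not change between visits or resting volume.
- A reader might see a six-year volume trend in "This extension phase will last six years". The extension is optional, its stated purpose is ventilator dependence, and no volume analysis is planned for it.
- A reader might extend the point to respiratory rate. Rate is not a volume, the height calculation does not cover it, and per-kg scaling would not address it.

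**Conclusion.** The point holds for between-session volume and ventilation. Children from age 2 are eligible, change over time is analysed without a control, and no adjustment for size or age is stated in the available text.

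On the assumed heights and scaling, growth alone adds about 4% to 16% over 6 months in children of roughly 87 to 150 cm. At 90 to 150 cm it adds about 13% to 46% if the baseline test was done 12 months before implant. The 18-month case is a maximum and applies only where an old clinical record supplies the baseline value.

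The effect on the group result cannot be fixed from the documents, because it depends on the number of growing children and on ventilator support during testing. This is a defect worth correcting in a secondary part of the analysis. It does not call the marked primary outcome or the within-session comparisons into question.

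**What to change.** In the SAP:

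1. Analyse between-session tidal volume and minute ventilation per kg body weight, or height-adjusted, alongside the unscaled values. Use body size measured at each testing visit, including baseline. Where the baseline value comes from clinical records, use the height and weight of that date.
2. Where forced expiratory values are summarised over time, give percent predicted or z-scores as well.
3. Show subjects under 18 separately in the between-session summaries.
4. Reconcile the protocol's 2 to 65 age range with the SAP's reference to adults. If only adults are intended, saying so removes most of the problem.

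The cost is SAP wording plus a height and weight at each testing visit. The schedule as printed already has a physical exam at Days 5, 14, 90 and 180, but none at screening or baseline, so size would have to be recorded there. The downside is that scaled values depend on body-size measurements or reference equations that can be unreliable in this population, which is why the unscaled values should stay in the report.
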